3.1. Study type

- Retrospective
- Prospective
- Combination Retrospective/Prospective

3.2. Single center / Multicenter

- Single center
- Multicenter

3.3 Check all the applicable boxes

- Medical records (re-use of data from healthcare, including AI)

- Case report
- Re-use data from research
- Evaluations of quality of healthcare (retrospective)
- Research with additional use of residual material from regular healthcare
- Research with re-use of human material from research or existing biobank
- De novo biobank
- Phase IV research
- Healthcare evaluation research (prospective)
- Research with medical devices
- Research with In Vitro Diagnostic Tests
- Other research, describe

Research with medical professionals comparing a new educational simulator with an educational video

4. Study population

4.1. Study population

- Adults (16 years and older)
- Minors (younger than 16 years)
- Incapacitated adults (16 years and older)
- Incapacitated minors (younger than 16 years)

4.2. Population (base)

As above; Our study will recruit from two populations for the expert and novice arms of this study. For the former, 10 experts who are experienced perfusionists/intensivists with more than 6 years of experience with ECMO will be included. For the novice arm, the population will include intensive care nurses & cardiothoracic surgery nurses who work at one of the academic hospitals in the Netherlands, with no prior experience with ECMO.

4.3. Inclusion criteria

Novices Inclusion Criteria

In order to be eligible as participant in this study in the **Novice Arm**, a subject must meet the following criteria:

1. Currently working as a nurse in one of the academic hospitals in the Netherlands
2. Provide informed consent

Experts Inclusion Criteria

In order to be eligible as participant in this study for the **Expert Arm**, a subject must meet the following criteria:

1. Currently working as an intensivist or perfusionist in one of the academic hospitals in the Netherlands
2. Provide informed consent

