The accuracy with which the predefined sequence of steps is performed by the participant, defined as number of mistakes made and time taken, and amount of prompts/assistance required from the expert perfusionist.

Secondary outcomes

[figure not shown]
Additional data include participants views on the advantages and disadvantages of virtual reality training in the context of ECMO.

Additional study parameters

Data will be collected on the participants age, gender, experience with ECMO, and experience with VR usage.

Study type

This will be a hybrid study, with an expert & novice face & content study, and contained within the novice group, a single blinded randomised controlled trial.

Study population

Our study will recruit from two populations for the expert and novice arms of this study. For the former, 10 experts who are experienced perfusionists/intensivists with more than 6 years of experience with ECMO will be included. For the novice arm, the population will include intensive care nurses & cardiothoracic surgery nurses who work at one of the academic hospitals in the Netherlands, with no prior experience with ECMO.

Methods

The study is broadly divided into two arms: expert (experienced perfusionists / intensive care staff) and novices (Intensive care staff who have no experience with ECMO) and is summarised in Figure 1.

Novice Arm (Randomised Controlled Trial)

Novice participants will be allocated a study ID from 1-50 at the point of recruitment and randomised by an online research randomiser (<https://www.randomizer.org/>) between the instructional video (control) group and VR-ECMO sim (intervention) group. The control group will watch a video in which a perfusionist explains how to perform a circuit check for an ECMO patient on VA ECMO. The participants are then individually assessed using a real ECMO machine and ECMO doll, whereby they are asked to repeat the steps that they have been trained in. This assessment is recorded on video to be assessed later by an expert assessor, and an expert perfusionist & assessor will be present during the assessment

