to provide prompts when a student is unsure how to perform a certain step. After completion of the assessment, the VR group will be asked to fill out an objective questionnaire (Appendix 2) based on the standardised USE questionnaire [2] to assess baseline characteristics such as prior experience/training and the usefulness, satisfaction, and ease of use of the VR training modality. Participants from the control group will be given the option to also perform the VR training, and subsequently fill a USE questionnaire about their experience with VR.

Expert Arm

Expert participants will not be randomised, and will all perform the VR-ECMO sim before completing the USE questionnaire. Their data will be used for the face and content validity portion of this study.

Randomisation

Participants in the novice arm will be randomly assigned to either interventional or control group, using <https://www.randomizer.org/> as stated above to generate a group allocation for the participant according to their study ID number.

Blinding

Participants will not be blinded as the differences in the differing nature of the intervention versus control group do not allow for this. Selected study personnel, including those physically facilitating both groups during the intervention phase will not be blinded, as again the study design does not allow for this. Study personnel who facilitate the physical assessment for the novice arm, perform data collection & analysis, including the expert assessor for the video recording, will be blinded.

Burden and risks

We do not foresee any risks or burdens incurred with participation, aside from mild nausea which may occasionally occur during a virtual reality experience. This typically subsides quickly once the head mounted display is removed.

Recruitment and consent

Our study will recruit from two populations for the expert and novice arms of this study. For the former, 10 experts who are experienced perfusionists/intensivists with more than 6 years of experience with ECMO will be included. For the novice arm, the population will include intensive care nurses & cardiothoracic surgery nurses who work at one of the academic hospitals in the Netherlands, with no prior experience with ECMO. We calculated a required sample size of 44 novice participants (22 per group) in order to likely achieve statistically significant results.

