The recruitment process will be performed by a combination of poster advertisements featuring a QR code where participants can sign up. These posters will be hung in areas where eligible staff are likely to gather e.g. break rooms. On the sign-up page, the participants will be asked to enter name and contact details, and then will be presented with the participant information form as attached as an appendix to this application. Once they have read this sheet, and agreed to it in the form by selecting 'I wish to participate' from multiple choice question, they will be taken to a further webpage where the option will be given to select a date on which to participate

1. Introduction and rationale

For intensive care staff in training, learning the steps in monitoring the function of an extracorporeal membrane oxygenator (ECMO) machine are fundamental concepts that form the basis on which their future practice will be built. The modality of this training is often practical in the form of an apprenticeship, shadowing experienced intensivists or perfusionists in order to learn their craft. We propose that if this initial training required more active participation in the form of a simulation, that trainees would learn these procedures more quickly and more reliably.

Over the past few years, emerging virtual reality (VR) applications have quickly gained broad attention within the medical field, including in cardiology and cardiothoracic surgery, as well as medical education more generally. Combining VR technology with head mounted displays (HMD), enables the design of a realistic, custom-built simulation in a 3 dimensional fully immersive environment [1]. Our group has developed a Virtual Reality (VR) simulation of the process of monitoring and performing a full circuit check for an ECMO patient. This Virtual Reality Extracorporeal Membrane Oxygenator Simulator (VR-ECMO sim) promises to update how we approach education of perfusionists and intensive care staff for their critical role.

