4.4 Exclusion Criteria

Novices Exclusion criteria

1. Failure to provide informed consent
2. Previous experience with ECMO equipment
3. Any reason that participants may not be able to perform the physical assessment

Experts Exclusion criteria

1. Failure to provide informed consent
2. Less than 6 years' experience with ECMO

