4.5 Sample size calculation

We calculated a required sample size of 32 novice participants (16 per group) in order to likely achieve statistically significant results in the Novice RCT arm. This is based on an alpha of 0.05, beta of 85, and a mean difference of 1. The expert group requires 10 participants in order to reasonably assess the face & content validity.

5. Methods

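### The expert criteria do not exclude people who helped develop the VR-ECMO sim, and no planned variable records such involvement, so some of the 10 expert ratings could be self-ratings and could be inflated.

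*Combined protocol and SAP*

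**What the plan says.** All references are to the combined protocol and SAP.

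- **Who qualifies as an expert.** Section 4.3 sets two conditions: informed consent, and "Currently working as an intensivist or perfusionist in one of the academic hospitals in the Netherlands". Section 4.4 excludes experts for lack of consent or for "Less than 6 years' experience with ECMO". No other section adds a condition.
- **Who built the simulator.** The Summary (Rationale) and section 1 both state: "Our group has developed a Virtual Reality (VR) simulation of the process of monitoring and performing a full circuit check for an ECMO patient".
- **How many experts, and why.** Section 4.5 says: "The expert group requires 10 participants in order to reasonably assess the face & content validity". It gives no precision, acceptance threshold or other basis for that number.
- **What the ratings are for.** The Summary (Expert Arm) says of the experts: "Their data will be used for the face and content validity portion of this study". Section 2 sets out to assess validity partly by comparing the questionnaire ratings of novices and experts. Section 7.2 lists the USE questionnaire as a secondary endpoint.
- **How people join.** The Summary and section 8.2 describe posters with a QR code and self sign-up. They describe no check on involvement in the project.
- **What is recorded.** Appendix 1 has ten baseline questions, on demographics, job, work and ECMO experience, gaming, VR and earlier training. None asks about a part in developing the simulator or running the study.

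**The concern.** Face and content validity is a stated aim, and expert judgement is a main support for it. Several USE items in Appendix 2 ask for an evaluation of the product itself: whether it was realistic, whether its quality satisfied the rater, and whether the rater would recommend it to colleagues. Someone who helped design or test the simulator and answers these items is rating their own work. That is not independent evidence, and the natural direction of any error is favourable.

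With 10 experts, each rating carries 10% of the expert mean. The plan sets no score that would count as adequate validity, so a modest inflation would meet no check. The expert figure is also set against the novice figure, so an inflated expert mean would move that comparison by the same amount.

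**Working it through.** **Step 1. Would a developer pass the written criteria?**

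| Requirement | Source | Does it screen out a developer? |
|---|---|---|
| Intensivist or perfusionist at a Dutch academic hospital | 4.3 | Only a developer of another profession or workplace |
| Informed consent | 4.3, 4.4 | No |
| Not below the ECMO experience threshold | 4.4 | Only a developer with too little ECMO experience |
| Independence from the simulator | Not stated | – |

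A developer with the right job and enough ECMO experience meets every condition. The documents do not give the developers' professions, so how many would qualify is unknown.

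**Step 2. Would the data show it?** The sign-up page collects names, and section 9.1 gives the PI and research coordinator a key table. They might recognise a colleague, but no rule says what should follow. The working data set carries no identifying information, and neither Appendix 1 nor Appendix 2 has an involvement item. An analyst could not separate involved raters, and a reader of the report could not know about them.

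**Step 3. How large could the effect be?** The figure of 10 experts has no stated inputs, so there is no calculation in the plan to reproduce. Let k be the number of developers among the 10, and d the points by which each rates above what an uninvolved expert would give. The total rises by k × d, so

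shift in expert mean = (k/10) × d.

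Neither k nor d is in the documents. Taking d = 0.5 to 1.0 point on the five-point scale as an assumption:

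| k | d = 0.5 | d = 1.0 |
|---|---|---|
| 0 | 0 | 0 |
| 1 | (1/10) × 0.5 = 0.05 | (1/10) × 1.0 = 0.10 |
| 2 | (2/10) × 0.5 = 0.10 | (2/10) × 1.0 = 0.20 |
| 3 | (3/10) × 0.5 = 0.15 | (3/10) × 1.0 = 0.30 |

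The scale also limits d: where an uninvolved expert would give 4, d cannot exceed 5 − 4 = 1. The formula applies to means. Section 7.4 also allows medians, and the shift in a median would depend on how the ten ratings are spread.

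**The case against.** The strongest reply is that this is a gap in wording and not a shown bias. No section says that a developer will be enrolled, and if none is, the shift is zero. The range above rests on invented inputs. USE is a secondary endpoint, novices rate the simulator too, and without an acceptance threshold a shift of a few tenths cannot be shown to change a conclusion. All of this stands, and it is why the point is put as a risk of unknown size. It does not remove the gap: the criteria admit developers, and nothing planned would reveal them.

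A reader might infer two stronger claims. The documents support neither.

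- **That other study roles would inflate the ratings too.** The Summary says "The control group will watch a video in which a perfusionist explains how to perform a circuit check" and "an expert perfusionist & assessor will be present during the assessment". These people may come from an eligible profession, but the presenter's ECMO experience and the assessor's profession are not given. None is described as having a stake in the simulator, and the presenter contributes to the comparator. Upward bias can be argued for developers only.
- **That the scoring of the randomised comparison is compromised.** Expert ratings feed only face and content validity. The number of prompts is part of the main endpoint in section 7.1, so keeping the prompter's role separate would be tidy. However, the Summary (Blinding) states that the facilitators of the physical assessment and the video assessor will be blinded, and Appendix 3 is a fixed 13-step form. Trying the simulator as an expert does not tell an assessor which arm a novice was in.

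A last objection is that the pool may be small. Section 4.3 covers all Dutch academic hospitals, but that is an eligibility line and does not show that recruitment will reach them all. This stands, and the fix needs a fallback.

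**Conclusion.** The point holds in a limited form. Sections 4.3 and 4.4 allow people who helped develop the simulator to be counted among the 10 experts who judge it, and the planned data would not identify them. Some expert ratings could therefore be self-ratings and could be inflated. It would go too far to say that the expert ratings are biased upward, because enrolment of developers is possible and not established.

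The shift in the expert mean is 0 if no developer enrols, and 0.05 to 0.30 point for 1 to 3 developers over-rating by 0.5 to 1 point. Both ranges are assumptions. The consequence is confined to face and content validity, a stated aim measured through a secondary endpoint. It is worth correcting because the correction is cheap and self-rating would be hard to detect afterwards.

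**What to change.** 1. Add an expert exclusion to section 4.4, for example: *Involvement in the design, scripting or testing of the VR-ECMO sim.*
2. Add one question to the expert sign-up page or Appendix 1, for example: *Have you had any part in developing the VR-ECMO sim or in running this study? If yes, please state which.* The question covers study roles so that they can be reported; the exclusion need not extend to them.
3. State a fallback in section 7.4: if 10 uninvolved experts cannot be found, report how many raters were involved and in what way, and repeat the expert summary without them. With 3 involved raters, for instance, the repeat would rest on 10 − 3 = 7.

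The cost is one line, one question and, if needed, one repeated table. The downside is a slightly smaller expert pool, which could be felt if recruitment is in practice local; the fallback covers that case.

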4.4 Exclusion Criteria

Novices Exclusion criteria

1. Failure to provide informed consent
2. Previous experience with ECMO equipment
3. Any reason that participants may not be able to perform the physical assessment

Experts Exclusion criteria

1. Failure to provide informed consent
2. Less than 6 years' experience with ECMO

4.5 Sample size calculation

We calculated a required sample size of 32 novice participants (16 per group) in order to likely achieve statistically significant results in the Novice RCT arm. This is based on an alpha of 0.05, beta of 85, and a mean difference of 1. The expert group requires 10 participants in order to reasonably assess the face & content validity.

5. Methods

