7.1 Main study parameters/endpoints

The accuracy with which the predetermined sequence of steps involved in an ECMO circuit check is performed by the participant. This is defined as number of mistakes made, and amount of prompts/assistance required from the expert perfusionist present at the assessment. Additionally, time to

accurately perform the predetermined endpoints/steps in the protocol of performing a circuit check as defined in Appendix 3.

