7.4 Analysis

Please describe how the analysis will be done for the outcome parameters.

R version 4.2.2 will be used for analysis. Continuous data will be assessed for normal distribution using a Q-Q plot and Shapiro Wilk test. The data will be described as median (IQR) or means (SD) and compared using either an unpaired t-test or the Mann-Whitney U test (whichever is appropriate according to the distribution) will be used to determine significance. Categorical variables will be reported as numbers (%) and compared using a chi-squared test or fishers exact test (whichever is appropriate according to the distribution). All baseline characteristics and outcome data will be compared using abovementioned tests. In case of confounding variables, we will correct for these using Analysis of Covariance (ANCOVA). A P-value of <.05 will be considered statistically significant.

8. Ethical considerations

8 Regulation statement

The study will be conducted according to the principles of the Declaration of Helsinki (64th WMA General Assembly, Fortaleza, Brazil, October 2013), Gedragscode Gezondheidsonderzoek 2022 and in accordance with ISO 27799:2016(en) standards, regulations and Acts.

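### The Summary requires 44 novices and section 4.5 requires 32, with no explanation, and the inputs in 4.5 are too incomplete to verify either figure

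*Combined protocol and SAP*

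**What the plan says.** Two places in the protocol report a calculated requirement for the novice randomised comparison.

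- Summary, Recruitment and consent: "We calculated a required sample size of 44 novice participants (22 per group) in order to likely achieve statistically significant results".
- Section 4.5, on the randomised novices: "We calculated a required sample size of 32 novice participants (16 per group) in order to likely achieve statistically significant results".

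Only section 4.5 gives inputs: "This is based on an alpha of 0.05, beta of 85, and a mean difference of 1".

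The main outcome has several components. The Summary describes accuracy as "defined as number of mistakes made and time taken, and amount of prompts/assistance required from the expert perfusionist". Section 7.1 says "This is defined as number of mistakes made, and amount of prompts/assistance required from the expert perfusionist present at the assessment" and then adds time to perform the steps. Section 7.4 leaves the choice between an unpaired t-test and a Mann-Whitney U test to the observed distribution, and sets the threshold: "A P-value of <.05 will be considered statistically significant". The Summary also allocates novice study IDs from 1 to 50, without calling 50 a sample size.

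**The concern.** Both statements describe a calculated requirement, for the same population and the same purpose, and both are current text. They cannot both be the requirement for one design. Neither refers to the other, and neither is worded as a target that includes a dropout allowance.

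This is the trial's only randomised comparison. A team that follows section 4.5 could stop at 32 and believe the plan fulfilled, while a reader of the Summary would find the trial 12 short. If the result is null, nobody could say from the protocol whether the trial reached its planned size or what power it had.

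A complete calculation in 4.5 would show which figure is right, but the one given there cannot be rerun.

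**Working it through.** **Inputs from the documents.** Alpha 0.05 and difference Δ = 1 (section 4.5); two equal groups of 16 (section 4.5) or 22 (Summary).

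**Assumptions.** The 85 is read as 85% power (beta 0.15). The SD appears nowhere, so every SD below is assumed. Sidedness is not stated; two-sided is used unless noted.

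**Step 1: can either figure be reproduced?** The normal-approximation formula is n per group = 2 × SD² × (z for alpha + z for power)² / Δ². With Δ = 1, two-sided alpha 0.05 and 85% power this is SD² × 2 × (1.960 + 1.036)² ≈ SD² × 17.96. Without an SD, no n follows. The result across assumed SDs:

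| Assumed SD | n per group, normal approximation | n per group, t-test (noncentral t) |
|---|---|---|
| 0.9 | 15 | 16 |
| 1.0 | 18 | 19 |
| 1.1 | 22 | 23 |
| 1.2 | 26 | 27 |
| 1.5 | 41 | 42 |
| 2.0 | 72 | 73 |

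Both 16 and 22 lie within this range, at different SDs. At SD 1 the totals are 36 or 38, which match neither stated figure.

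**Step 2: does dropout link them?** Setting 32 / (1 − d) = 44 gives d = 1 − 32/44 = 27.3%. No section mentions such a loss, or any other.

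**Step 3: could one set of inputs give both?** No. With test, sidedness, power and difference fixed, one SD gives one n. For a t-test at 85% power, the SDs that round up to exactly 16 and 22 per group are:

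- two-sided: 0.882 to 0.913 for 16, and 1.055 to 1.081 for 22;
- one-sided: 0.996 to 1.031 for 16, and 1.188 to 1.217 for 22.

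One SD can give both only if something else changed between the two calculations. With SD 1, for example:

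- two-sided normal approximation: 80% power gives 2 × (1.960 + 0.842)² = 15.70, so 16; 90% power gives 2 × (1.960 + 1.282)² = 21.01, so 22;
- at 85% power: a one-sided t-test needs 15.10, so 16; a two-sided Mann-Whitney test at relative efficiency 0.864 needs 18.97 / 0.864 = 21.95, so 22.

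The documents do not say that any of this happened.

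**Step 4: what the choice could mean for power.** Power comes from the noncentral t distribution with 2n − 2 degrees of freedom and noncentrality (Δ/SD) × √(n/2). For the Mann-Whitney test, n is replaced by efficiency × n, with efficiency 0.955 (normal data) or 0.864 (the large-sample lower bound for a shift between continuous distributions). Two-sided alpha 0.05:

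| Test | Assumed SD | Power at 32 | Power at 44 |
|---|---|---|---|
| t-test | 0.8 | 93% | 98% |
| t-test | 1.0 | 78% | 90% |
| t-test | 1.5 | 45% | 58% |
| Mann-Whitney, 0.955 | 1.0 | 76% | 89% |
| Mann-Whitney, 0.864 | 0.8 | 89% | 96% |
| Mann-Whitney, 0.864 | 1.0 | 72% | 85% |
| Mann-Whitney, 0.864 | 1.5 | 39% | 52% |

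Simulating the Mann-Whitney test with normal data and SD 1 (40,000 trials) gives about 75% and 88%, close to the 0.955 row.

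**The case against.** The strongest reply accepts the conflict but disputes its weight. Enrolling 44 meets both statements, so harm arises only if 32 is used. This is an education study in professionals, with mild nausea as the only foreseen risk. The beta of 85 is an obvious slip, section 7.4 does narrow the test to two candidates, and a P-value threshold of .05 is usually read as two-sided. Incomplete inputs alone would be a reporting gap. That last point is fair: the 44/32 conflict carries the finding.

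Four further points stand in part.

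- The power figures rest on SDs that the documents do not supply. They show only that the choice can matter.
- The non-overlapping SD ranges restate the inconsistency and are not separate evidence.
- The 0.864 efficiency is a bound for continuous data. Mistakes and prompts are small counts with ties (Appendix 3 lists 13 yes/no steps), so it is not a guaranteed floor here.
- The correction may cost more than wording if the team is currently working to 32.

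One could also argue that section 4.5 governs and the Summary is simply out of date. The protocol gives neither place precedence, and 4.5 would remain unverifiable. None of this removes the contradiction.

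**Conclusion.** The concern holds. The protocol gives two different calculated requirements for one comparison, 44 and 32, so at least one is wrong as written. The difference is 12 participants: 27% of 44, or 37.5% of 32. That much comes from the documents alone.

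Neither figure is shown to be an arithmetic error, because each can be reached under plausible but unstated inputs. The SD, endpoint and unit are absent, sidedness is unstated and the test is left open, so the power at either number is unknown. This must be fixed, since the trial's planned size depends on it.

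**What to change.** Recover the inputs behind both figures, then state one sample size in the Summary and in section 4.5. If 44 is 32 plus a dropout allowance, say so and give the rate. Replace the beta of 85 with the intended power (or beta 0.15 if 85% is confirmed). Suggested wording for both places:

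> N novices (n per group) give [x]% power at a [one/two]-sided alpha of 0.05 to detect a difference of 1 [unit] in [endpoint], assuming an SD of [s] from [source], using [t-test / Mann-Whitney test].

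If the recovered inputs do not give 85% power at the number kept, report the power that number does give under the named test. This avoids enrolling beyond the figures already in the protocol. A clause saying what the ID range 1 to 50 represents would remove a possible third reading.

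**Cost.** If the number kept is the one the team already works to, the change is wording, submitted under section 12 where it counts as an alteration. If the team works to 32 and 44 is kept, 12 more novices are needed. The stated power may become less favourable: keeping 32 with an assumed SD of 1 and two-sided testing would mean about 78% for a t-test, or roughly 72% to 76% for a Mann-Whitney test before any effect of ties.
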